Pregnancy outcomes and medical costs according to gestational diabetes mellitus diagnostic criteria: randomized prospective study. POMECS study.

Protocol ID: 00003

Approval Number: 11/09/2016

Version: 8th January 2018

Due to Hyperglycemia and Adverse Pregnancy Outcomes study results, a new gestational diabetes mellitus (GDM) diagnostic criteria was defined using a one-step approach (75-g oral glucose tolerance test -OGTT-) ¹

However, not all scientific societies have accepted and have implanted this new diagnostic criteria. The lowest glycemia cut-off of this criteria regarding the two-step approach entails an increase in GDM incidence with discordant studies about its cost-effectivity ²⁻⁴.

It will be assessed if pregnancy outcomes and medical costs are different depending on diagnostic criteria used.

RESEARCH DESIGN AND METHODS

The POMECS study is a randomized, parallel group trial, conducted in Spain. The Ethics Committee at Hospital Universitari Mútua Terrassa (Spain) approved the study.

Participants:

All pregnant women with follow-up of their gestation at Hospital Universitari Mútua Terrassa (Spain), at first antenatal visit, will be proposed to participate in the study.

Inclusion Criteria:

- Age 18-50 years
- No expectation that the participant will be moving out of the area of the clinical centre during the next year
- Informed Consent Form signed by the subject

Exclusion Criteria:

- Pre-existing type 1 or 2 diabetes
- Advanced human immunodeficiency virus infection (on medications that cause hyperglycemia), severe liver disease, gastric bypass surgery or other illnesses/surgeries that preclude them from drinking the glucose solution.

Randomization:

All pregnant women without a former diagnosis of diabetes mellitus will be considered for gestational diabetes mellitus (GDM) screening at 24–28 weeks of gestation.

Women with risk factors for diabetes at their initial prenatal visit will be screening at 9-12 weeks of gestation. Risk factors are: Age >35years, obesity (body mass index $\geq 30\text{kg/m}^2$ or $>27.5\text{kg/m}^2$ in Asian Americans), first-degree relative with diabetes and high-risk race/ethnicity (e.g., African American, Latino, Native American, Asian American, Pacific Islander).

At the time of GDM screening, patients will be assigned a number by a random number generation program (ratio 1: 1) that will classify them to one of the following two groups:

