- Experimental Group (One-step): International Association of Diabetes and Pregnancy Study Groups (IADPSG) Criteria.

Performing a fasting 2 hour 75g OGTT. The diagnosis of GDM is made if at least one or more values are \geq : Fasting 92, 1-hour 180, or 2-hour 153 mg/dL.

- Active Comparator (Two-step): National Diabetes Data Group (NDDG) Criteria

Step 1: Performing a 1h 50-g glucose load test (nonfasting). If the plasma glucose level measured 1 h after the load is \geq 140 mg/dL, proceed to a 100-g OGTT.

Step 2: 100-g OGTT. The diagnosis of GDM is made if at least two of the following four plasma glucose levels measured (fasting, 1 h, 2 h, 3 h after the OGTT) are \geq : 105mg/dl, 190mg/dl, 165mg/dl and 145mg/dl respectively.

If only one value is exceeded, 100g OGTT will be repeated 2-3weeks after.

Pregnant women without GDM diagnosis at third trimester of pregnancy will repeat GDM screening (according previous randomization) if it appears macrosomia or/and polyhydramnios in the follow-up.

GDM diagnosed women will be managed with diet and self-monitoring of blood glucose. Insulin will be added according to the local protocol⁵. All women will receive routine prenatal care (without differences between randomized groups).

Outcomes

Primary outcome Measures:

Large for gestational age (LGA): Infant birthweight >90th centile using customized growth curves. Time Frame: At birth of infant.

Secondary Outcome Measures:

1. Infant outcomes

- Small for gestational age (infant birthweight <10th centile using customized growth curves); macrosomia (infant birthweight \geq 4kg), Neonatal obstetric trauma (shoulder dystocia, clavicle fracture, brachial plexus injury, intrapartum asphyxia), Congenital anomalies (Coding of EUROCAT), Pregnancy loss (Miscarriage, stillbirth, neonatal death)

Time Frame: At birth of infant

- Neonatal hypoglycaemia (neonatal plasma glucose levels <2.5 mmol/L in the first 24 hours of life and <2.8 mmol/L thereafter), Neonatal hypocalcemia (neonatal calcium levels <7mg/dl), Neonatal hyperbilirubinemia (hyperbilirubinemia treated with phototherapy), Neonatal polycythemia (hematocrit from a peripheral venous sample >65 percent), Respiratory Distress Syndrome (onset of progressive respiratory failure shortly after birth, in conjunction with a characteristic chest radiograph -after ruling out other causes-), Hypertrophic cardiomyopathy (increased left ventricular -LV- wall

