thickness ≥ 15 mm imaged anywhere in the LV wall -by transthoracic echocardiography-), NICU admission (NICU admission for treatment or surveillance), neonatal hospital stay (Length of hospital stay –days-).

Time Frame: at infant hospital discharge.

- Perinatal mortality (infant deaths that happen at less than 7 days of age and fetal deaths with a gestational age of 28 weeks or more). Time Frame: First 7 days postpartum.

2. Maternal outcomes

-Hypertension in pregnant: worsening of chronic hypertension, gestational hypertension and preeclampsia. Time Frame: First 3 months postpartum

- Polyhydramnios (Amniotic fluid index ≥ 25 cm). Time Frame: At birth of infant.

- Cesarean section delivery of a baby through a surgical incision in the mother's abdomen and uterus. Time Frame: At birth of infant.

- Maternal hospital stay: Length of hospital stay (days). Time Frame: at maternal hospital discharge.

- Questionnaires: Evaluation of Mediterranean diet adherence using Mediterranean Diet Adherence Screener (MEDAS) questionnaire. Evaluation of health-related physical activity using IPAQ questionnaire. Time Frame: up to 12-14weeks from last menstrual period.

3. Gestational age at delivery: Gestational age was defined as completed weeks based on last menstrual period or the earliest ultrasound assessment if discordant. Time Frame: At birth of infant.

4. Medical cost: economic cost include laboratory costs; glucose bottles (50 g, 100 g and 75 g); pharmaceutical expenditure (exact insulin doses consumed, total pens, needles, strips); medical visits during pregnancy and postpartum (endocrinologist, educational nurses, obstetrician and midwives); total number of tests (ultrasounds, cardiotocography records); cost of intensive care unit admissions (Length of stay and complexity) and total hospital admission costs. Time Frame: First 3 months postpartum

Statistical analysis

Sample size (n=3,644) was calculated to detect a 20% decrease rate of LGA (primary outcome), assuming baseline rate of 16.5% ($\alpha=0.05$ and $\beta=0.80$). This decrease rate was obtained from *St Carlos Gestational Diabetes Study*, carried out in Spanish population which compared Carpeten-Coustan criteria vs IADPSG criteria³. Since we will use NDDG criteria (vs. IADPSG), baseline LGA incidence was obtained from Spanish Multicentre Study⁶.

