Results will be presented as means \pm standard deviation in normal distribution, median [interquartile interval (IQI)] in non-normal distribution or percentages. Normal distribution will be tested for each variable using the Kolmogorov test.

Student t test will be used for normally distributed variables and the Mann-Whitney U test for non-normally distributed variables between two independent groups.

Proportions will be compared using a Pearson's chi-square or Fisher exact test as appropriate.

We will use logistic regression analyses or multivariate linear regression (as appropriate) to estimate the ratio of the probability [I-TDS(1)] of occurrence of an adverse event (primary and secondary outcomes) with 95% CIs by experimental group versus control group adjusting for confounding factors (age, smoke habit, weight, multiparity) P values <0.05 were considered statistically significant. All statistical calculations will be performed with the STATA 14.0 statistical package.

REFERENCES

1. Metzger, B. E. *et al.* Hyperglycemia and adverse pregnancy outcomes. *N. Engl. J. Med.* **358**, 1991–2002 (2008).
2. Meltzer, S. J., Snyder, J., Penrod, J. R., Nudi, M. & Morin, L. Gestational diabetes mellitus screening and diagnosis: A prospective randomised controlled trial comparing costs of one-step and two-step methods. *BJOG An Int. J. Obstet. Gynaecol.* (2010). doi:10.1111/j.1471-0528.2009.02475.x
3. Duran, A. *et al.* Introduction of IADPSG criteria for the screening and diagnosis of gestational diabetes mellitus results in improved pregnancy outcomes at a lower cost in a large cohort of pregnant women: the St. Carlos Gestational Diabetes Study. *Diabetes Care* **37**, 2442–50 (2014).
4. Corcoy, R., Lumberras, B., Bartha, J. L., Ricart, W. & Grupo Español de Diabetes y Embarazo. New diagnostic criteria for gestational diabetes mellitus after the HAPO study. Are they valid in our environment?. *Endocrinol. Nutr.* **57**,

277–80

5. Asistencia a la gestante con diabetes. Guía de práctica clínica actualizada en 2014. *Av. en Diabetol.* **31**, 45–59 (2015).
6. Ricart, W. *et al.* Potential impact of American Diabetes Association (2000) criteria for diagnosis of gestational diabetes mellitus in Spain. *Diabetologia* **48**, 1135–41 (2005).

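### The adjusted logistic model is planned for every binary outcome with no sparse-event method; for very rare secondary outcomes the promised odds ratio and 95% CI may not exist or may be unstable.

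*Combined protocol and SAP*

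**What the plan says.** The Statistical analysis section of the combined protocol and SAP describes the adjusted analysis once, for all outcomes: "We will use logistic regression analyses or multivariate linear regression (as appropriate"). The model estimates a ratio for the "occurrence of an adverse event (primary and secondary outcomes) with 95% CIs", experimental versus control, with age, smoking, weight and multiparity as covariates. The natural reading of the qualifier is that it separates binary from continuous outcomes.

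The same section compares unadjusted proportions by Pearson's chi-square or Fisher's exact test. It sets no minimum event count, smaller covariate set, exact or penalised model, or rule for an arm or covariate level without events.

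The Outcomes section, under Infant outcomes, lists several conditions that may be very uncommon. One is "Perinatal mortality (infant deaths that happen at less than 7 days of age", together with late fetal deaths. Others are hypocalcemia, polycythemia and hypertrophic cardiomyopathy. No expected rate is given for any secondary outcome.

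**The concern.** The sample size was set for LGA, an outcome with hundreds of expected events. The same five-slope model (group plus four covariates) is then applied to outcomes that may have only a handful.

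Maximum-likelihood logistic regression has no finite group estimate when one arm has no events. When a binary covariate level has none, that coefficient is infinite, and a standard fit either fails to converge or drops the level. Fisher's test still gives a p-value, but not the adjusted ratio and interval that the plan promises.

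Without a rule, the analyst must decide after seeing the sparse data whether to drop covariates, change method or leave the outcome out. Those choices can give different intervals for outcomes such as perinatal death.

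**Working it through.** **1. Inputs from the plan.** Total N is 3,644; allocation is 1:1 ("assigned a number by a random number generation program (ratio 1: 1")), so 1,822 per arm. The LGA calculation is "assuming baseline rate of 16.5"%, with a 20% relative decrease to 13.2%, α = 0.05 and power 0.80 (printed as β).

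**2. The plan's own figure.** With p̄ = (0.165 + 0.132)/2 = 0.1485 and a two-sided test:

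n per arm = [1.960 × √(2 × 0.1485 × 0.8515) + 0.842 × √(0.165 × 0.835 + 0.132 × 0.868)]² / 0.033² = 1,821.5, rounded up to 1,822, so 3,644 in total.

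This matches the plan.

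**3. Assumptions.** Event rates p of 0.1% to 1%; 15% smokers (range 10% to 30%); 50% multiparous; no true group or covariate effects. None of these is in the documents.

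**4. Formulas** (Poisson approximation).
- Expected events: λ = 3,644p. Events per slope: λ/5.
- No events in at least one arm: 1 − (1 − e^(−1,822p))². At 0.1%: e^(−1.822) = 0.162, giving 1 − 0.838² = 0.297.
- No events among smokers: e^(−0.15λ). At 0.1%: e^(−0.547) = 0.579.
- No events in an arm or in a level of smoking or parity: 1 − Σₙ Pois(n; λ) × (1 − 2 × 0.5ⁿ)² × (1 − 0.85ⁿ − 0.15ⁿ), summed over n ≥ 1. The squared term covers arm and parity, and the last term covers smoking.

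**5. Results.**

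| Rate | Expected events | Events per slope | An arm has none | No smoker has one | Arm or covariate level has none (10% to 30% smokers) |
|---|---|---|---|---|---|
| 0.1% | 3.6 | 0.7 | 30% | 58% | 70% (78–55%) |
| 0.2% | 7.3 | 1.5 | 5% | 34% | 38% (51–18%) |
| 0.3% | 10.9 | 2.2 | 0.8% | 19% | 20% (34–5%) |
| 0.5% | 18.2 | 3.6 | <0.1% | 6.5% | 7% (16–0.5%) |
| 1% | 36.4 | 7.3 | ~0% | 0.4% | 0.4% (2.6–0%) |

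Simulated trials under the same assumptions scatter around the last column: 68–71%, 37–43%, 17–21% and 5–7% at the first four rates.

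**6. Precision when the group estimate exists.** In 1,000 simulated trials per rate, the median ratio of upper to lower 95% limit was about 81 at 0.1%, 20 at 0.2%, 12 at 0.3% and 3.7 at 1%.

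**7. What an event-free smoker level does to the group effect.** Dropping smokers then discards about 0.15 × 3,644 = 547 women but no events. In 60 simulated trials per rate with at least six events, at 0.2% and 0.3%, the fit without smokers was compared with a fit on all women without the smoking term. The group log odds ratio moved by about 0.01 on average (largest 0.06), and the ratio of standard errors stayed within 0.999–1.002.

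**8. The alternative.** Firth-penalised logistic regression with the same five slopes (300 simulated trials per rate, 0.1% to 0.5%) gave a finite group estimate in every trial with at least one event. That is 98.7% to 100% of all trials. Wald interval coverage was about 95% to 99%.

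**The case against.** Several points on the other side stand.

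- **Rates are assumed.** The difficulty is common at about 0.2% or below, moderate at 0.3% and small from 0.5% upward. A reader might infer that the adjusted analysis will often fail across the secondary outcomes. The documents give no rates to support that.
- **A lost covariate level is not a lost treatment effect.** A reader might infer that dropping about 547 smokers distorts the comparison. Step 7 shows that it barely moves it. The measure of a missing group estimate is the event-free arm, at 30%, 5%, 0.8% and under 0.1%; the larger figures describe a fit that cannot be completed as written.
- **Nothing shows that a level would be lost unnoticed.** A reader might infer this from how software behaves. The documents do not say how such a result would be handled or reported.
- **Nerve injury is a weak example.** The plan lists "brachial plexus injury, intrapartum asphyxia" with shoulder dystocia and clavicle fracture under neonatal obstetric trauma. Analysed as one outcome, that has more events than any single component.
- **Fisher's test remains valid** for the unadjusted comparison in a 1:1 randomised trial, so what is lost is the adjusted ratio and its interval. No method makes an interval from about four events narrow.

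These points limit the size of the concern but do not answer it. The plan promises an adjusted ratio with a 95% CI for every outcome and says nothing on what to do when the model cannot supply one.

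**Conclusion.** The concern holds for very rare binary secondary outcomes only, and it is minor. If perinatal mortality, hypertrophic cardiomyopathy, polycythemia or hypocalcemia occur at 0.1–0.2%, the group odds ratio has no finite estimate in about 30% to 5% of trials, and the full model cannot be fitted as written in about 70% to 37–43%. At 0.5% those figures fall to under 0.1% and 5–7%. The event-free-arm figures rest on the assumed rates and no true group effect. The wider figures also rest on 15% smokers and 50% multiparous. That the logistic model is ordinary maximum likelihood is inferred, because no other version is named. The LGA sample size and analysis, and those of the common outcomes, are sound on this point.

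**What to change.** Add a short rule to the Statistical analysis section:

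- For any binary secondary outcome with fewer than a fixed total number of events, for example 50, estimate the adjusted odds ratio by Firth-penalised logistic regression with the same four covariates, and state the type of interval.
- Report event counts and percentages by arm and Fisher's p-value alongside.
- If neither arm has an event, report counts only; Firth cannot help there.
- Keep the planned model for LGA and the common outcomes.

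A threshold of 50 is 10 events per slope, or a rate of 50/3,644 = 1.4%. It is a conservative rule of thumb: the failures computed above are already few at 0.5%. What matters is that the number is fixed in advance and that a single method is named, so the choice between an adjusted and an unadjusted measure is not left until the data are seen.

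The cost is a few lines of text, an add-on Stata command and a different method for the rarest outcomes. Their intervals will stay wide. The sample size does not change.
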